The cost of La Comunidad will be separated into research and intervention costs. Research costs will be excluded from the economic evaluation. The intervention costs will be classified into direct medical, direct nonmedical, and indirect costs. The identification and measurement of the cost of a health prevention program can be determined from four different perspectives: individual, health care provider, third party payer (including large health care systems, insurers, government, etc.), and society. In La Comunidad, we will adopt the perspectives of individuals, third party payers and society in three separate analyses, as all three perspectives will influence successful dissemination. From the individual's perspective, the total cost estimation will include participants' out of pocket expenses, and cost associated with travel time and missed working days due to illness. In the third party payer perspective, we will only include the direct medical costs (including the intervention) in the total cost estimation. The participants' out of pocket expenses and indirect cost such as missed working days will not be included. In the societal perspective, the total cost will constitute all direct and indirect costs incurred by participants and the third-party payers. In order to assure comparability to both DPP and HELP PD, we will apply similar criteria for determining costs. Direct medical costs

include the cost of implementation and maintenance of the intervention and the cost of utilization of medical services by study participants. We will assess the personnel resource use and cost in the comparison and lifestyle intervention groups, including personnel time, mailings and telephone calls using standardized questionnaires administered to the staff. Unit cost for personnel will be calculated as the median salaries of personnel employed by the study team with a fringe benefit rate. Unit costs of health education materials will be based on actual reproduction rates. Unit costs of laboratory tests will be based on the Center for Medicare and Medicaid Services (CMS) reimbursement rates. Overhead costs will be estimated by multiplying personnel costs related to the intervention by the institutional rate negotiated with NIH. The proposed intervention may have an impact on the use of medical services outside La Comunidad, including hospital, emergency department, outpatient clinic, physician office, and medications. A resource utilization questionnaire will be administered to participants semi-annually, inquiring about hospital admissions, length of stay, number of emergency department (ED) and physician office visits, and medications used. Unit costs of hospital admissions, hospital days, ED visits, and physician's office visits will be based on CMS average reimbursements, respectively. Unit costs of medications will be based on average wholesale prices available on the internet. This questionnaire will also inquire about purchases of equipment -and memberships in health facilities and other related direct nonmedical costs. These and other direct nonmedical costs including transportation to clinic, waiting and participation time will be estimated using the DPP direct nonmedical cost estimation methods²³. Indirect costs include participants' productivity losses such as working days missed due to health reasons, and will be estimated based on the median hourly wage, as in DPP²³.

I. Documentation

La Comunidad will develop a Manual of Procedures (MOP), an LHA Intervention Manual (IM), and participant manuals. More comprehensive than this protocol, the MOP will include the protocol as its first chapter and will provide the specifics of study conduct. It will be modified during the study if any changes in the data forms and data collection techniques are necessary. The MOP will contain detailed information on the study's conduct, including comprehensive descriptions of recruitment, enrollment, randomization, data collection, monitoring and follow-up procedures. It is meant to be the "how-to" manual and the source of information regarding the day-to-day operation of the study. A separate manual, the IM, will be developed for LHA training, intervention conduct, and standardization purposes. Comprehensive detailed guidelines for the dietary, exercise and behavioral interventions will be in the IM and serve as the basis for the intervention monitoring system. Participant manuals will supplement the IM. The MOP and IM will be developed prior to the first training session.

J. Database Management System

To facilitate data transfer and preserve records that can be audited, we plan to use paper forms for data collection and remote data entry via an internet-based web browser interface. As in HELP PD, electronic data will be managed centrally, with a feedback mechanism through e-mail and web-based reporting. Data reside on the server in a Microsoft SQL Server relational database. Cold Fusion middleware, a web application development tool, will be used to link the web-based forms interface to the SQL Server database. SAS/Access is used to translate data from the SQL Server database to SAS datasets, which reside on a UNIX-based Sun

Microsystems server. Validation checks are applied during the data entry process. Insofar as possible, checks are programmed and made as the staff enter data from each form, so that errors on the forms are corrected on-site at this early stage. These include intra-form and inter-form checks for consistency of responses, range checking, and checks for required fields and skip patterns.

Our internet based data entry system will protect confidentiality and data security. A very high level of data encryption during transmission coupled with the use of acrostics and study ID numbers, rather than subject names, provides adequate data security. The use of text containing identifying information will be avoided. We will implement standard protection against computer hackers. Our site will offer neither special challenges nor sensational data for hackers. This lack of inducements may decrease the chance that it will be targeted.

K. Methods for Ensuring High Data Quality and Integrity

Quality control (QC) is a shared responsibility among all staff. The impact of La Comunidad on diabetes in the Latino population depends on the integrity of its implementation: maintaining randomization integrity, assessing participant eligibility accurately, recording dropouts and adherence, measuring outcome variables without bias, preventing premature leaks of results, monitoring and assessing protocol adherence, and avoiding biases in the analyses. In order to deal effectively with these important issues, adaptations of models for QC systems currently utilized in many of our ongoing studies will help us establish the QC system for La Comunidad. QC procedures will be devised to monitor screening, data collection, follow-up, clinical and biochemical measurements, forms control and data entry procedures, implementation of the intervention and overall operations.

IV. Analytical Plan

All statistical analyses will be conducted by the Research Core of the Maya Angelou Center for Health Equity. The main hypothesis being tested involves evaluating the mean differences in changes in HbA1c at one year. Secondary outcomes include changes in clinical characteristics and biochemical lab results and biomarkers of insulin sensitivity. Statistically, all of these analyses could be treated in a similar fashion after appropriate transformations are made to satisfy assumptions made about the distribution of residuals. We will apply a repeated measures analysis of variance to changes (collected across the planned visits at 6, 12, 18, and 24 months) to address intra-individual correlations, which accommodates interim testing and allows participants with incomplete patterns to contribute to the analysis and evaluation²⁴. Our analysis adopts the intention-to-treat approach. Inference for primary comparisons will be two-sided, with significance level alpha = 0.05. We will use repeated measures analysis of covariance in which indicators for visit are included to control for systematic temporal differences that may occur that are common to both intervention conditions. We test differences from baseline (rather than using baseline levels as a covariate in analyses of post-randomization values), as it is these differences that are the focus of our intervention and to limit the bias associated with estimates from regression models that include fallible covariates. Random effects terms will be used to model differences as these have been shown to yield inferences of more appropriate size than fixed effect models. Compound symmetry models will be used to model intra-subject

longitudinal covariance and models will be fitted via maximum likelihood. The primary comparison will be based on a Wald statistic. We will not include additional covariates or stratification in the primary comparison, however, we will describe any chance differences between cohorts and, in supporting analyses, covary comparisons on any baseline factors that appear to be unbalanced. When we are developing the ANCOVA models, we will determine whether the assumptions of general linear models are satisfied. Diagnostics and residual plots will be reviewed to ensure that the assumptions are met. Should assumptions be violated, transformations of the outcome data will be considered: the order of the priority in choosing a transformation will be to satisfy the (1) linearity assumption, (2) homogeneity assumption (homoscedasticity), and (3) normality assumption. As mentioned above, secondary (supporting) analyses will assess the influence of covariates on the mean differences and to explore whether mean differences vary over follow-up time (using interaction terms). In addition, we will explore the homogeneity of LHAs with respect to outcome measures using hierarchical mixed models in which LHAs are coded as random effects and participant data are nested within LHAs. Such models will allow us to place confidence bounds on the contributions of LHA differences to overall variability.

Sample Size and Power

In this section we justify our plans to recruit and follow 225 participants who will be randomized with equal probability to either the intensive lifestyle intervention or individual education arm. Our goal is to provide greater than 80% statistical power to detect an average difference of .25 standard deviations from baseline in HbA1c between the two groups at one year. With a sample size of 225 participants, we will have 85-88% power to detect a net intervention effect of .25%. These estimates include allowance for a 5% loss to follow-up rate every 6 months. Although the DPP has not published any data that allow us to estimate the standard deviation and longitudinal correlation of HbA1c, similar studies conducted for a longer period of time have estimated the average change in A1c to be .74% with a standard deviation of 1.25% for an effect size of .59.

V. Human Subjects Protection

A. Potential Risks to Subjects

The risk to participants is modest, consisting primarily of the risk of increased moderate physical activity. Adoption of a vigorous activity regimen can increase the risk of cardiovascular events in sedentary individuals. The other minor risks include risks associated with phlebotomy and confidentiality concerns. Phlebotomy carries a small risk of vasovagal syncope (fainting), hematoma formation and phlebotomy site infection.

B. Protection against Risks

Approval to proceed with this project will be sought from the WFUHS Institutional Review Board (IRB). We will submit an informed consent document, including HIPAA authorization, as part of our application for approval. The risks inherent in the project consist mainly of the small risk of a cardiovascular event associated with adopting a moderate intensity physical activity regimen, the risk of phlebotomy and confidentiality concerns. The risk of the physical activity

program will be minimized by focusing on moderate, as opposed to vigorous, activity and by stressing a start slow and increase slowly approach. We will be encouraging participants to adopt brisk walking as the foundation of their activity program and we will educate participants about the potential risks of increased activity. Potential participants will also be screened using the Physical Activity Readiness Questionnaire. Persons who screen positive will be required to obtain medical clearance from a primary care provider prior to participation. All potential participants will be encouraged to discuss participation with their usual physician prior to enrolling in La Comunidad. An informational brochure will be developed so that potential participants can review and discuss the program with their physician, and if he/she does not have a physician, he/she will be referred to a source of care in the community. This brochure will be provided to the IRB for approval prior to use. The risk of phlebotomy will be minimized through the use of trained professional phlebotomists. The blood volume obtained at any phlebotomy will be no more than 20 mL. Risks related to inadvertent release of confidential information will be minimized through adherence to best practices for data collection and management. All research staff will be trained in methods for assuring participant confidentiality and safety. The information we are collecting is not of a particularly sensitive nature and we will follow exacting procedures to maintain confidentiality of the participant level data. Identifying information will be kept separate from research data and will be linked only by a participant ID, generated so as to be independent of any identifying information. The linking report and personal identifying data will be destroyed after completion of the study. No identifying information will be released in any published reports.

C. Potential Benefits and Importance of Knowledge to be Gained

The potential direct benefits to participants include the decreased risk of developing diabetes and cardiovascular disease. In the DPP, the risk of developing diabetes was 11% per year in the “usual care” group. This risk was decreased by over 50% in the intensive lifestyle intervention group. In the HELP PD study, the group-based intervention showed significant weight loss and improvements in glucose. La Comunidad is designed to move the intervention tested in HELP PD into the Latino community, improving diabetes prevention efforts. The development of diabetes carries with it significant morbidity and mortality risk. Persons with diabetes are at an increased risk of cardiovascular diseases, in addition to increased risk of blindness, kidney failure and lower extremity amputation. The small risks of an acute cardiovascular event triggered by moderate physical activity should be far offset by the substantial potential benefit of diabetes prevention. Other potential benefits to subjects may include improved quality of life and satisfaction with self-image. Little direct benefit is expected to others; however, as persons with diabetes may impose some care-giver burden on others due to their need for frequent medical attention, it is possible that there will be some benefit related to decreased care-giver burden.

The knowledge to be gained in the proposed trial relates to our ability to implement evidence-based lifestyle interventions in different populations. As discussed above, the risks of diabetes are substantial and the potential benefits for preventing diabetes are great at the societal level; hence, the risk that participants will assume by participating in this program should be offset by the potential for public health benefit that would occur following dissemination of a successful diabetes prevention program. Furthermore, this approach could also serve as a model for other

community-based health promotion programs in the Latino community, further enhancing the potential societal benefit of the proposed project.

VI. Subject Recruitment Methods

Participants will be recruited to La Comunidad using a mixture of advertising, community recruitment events, and provider referrals from healthcare sites. Given the unique role that churches play in the Latino community, we plan to initiate our recruitment efforts there. Currently, 5 local churches have agreed to serve as partners for this effort and we plan to identify additional churches in the future. We will also request a list of adult patients seen in outpatient primary care clinics at Wake Forest Baptist Medical Center who have no diagnosis of diabetes and for whom ethnicity is recorded as "Hispanic or Latino". This list will be requested from the Enterprise Data Warehouse through the Translational Science Institute and will be used to generate mailings to potential participants. As a part of this data request, we will also request a limited waiver of HIPAA authorization from the IRB and the list generated will only be used under this waiver. We will also plan to post flyers and posters in the Downtown Health Plaza space to supplement these efforts. All flyers, brochures, letters, and other recruitment materials will be submitted to the IRB of Wake Forest University Health Sciences for approval prior to use. Signed informed consent will be obtained from all participants prior to conducting any screening activities. Copies of the signed consent forms will be provided to all participants. The original signed forms will be kept in study files.

We plan to identify local adults who identify themselves as Latino who are at high risk for developing type 2 diabetes. Primary inclusion criteria include BMI of 25-45 kg/m² and evidence of pre-diabetes (based on HbA1c). Candidates will also be screened for co-morbid conditions that would make physical activity unsafe or limit participation in the study, including recent history of an acute cardiovascular disease event, clinical history of diabetes mellitus, cancer or other conditions limiting life expectancy, and major psychiatric or cognitive problems, including depression. For safety purposes, potential participants will also be screened using the Physical Activity Readiness Questionnaire (PAR-Q). Persons who screen positive on the PAR-Q will be required to obtain medical clearance from a physician prior to participation.

VII. Informed Consent

Signed informed consent will be obtained from each subject after pre-screening but prior to the collection of any blood samples or other physical measurements. Participants who speak Spanish as their primary language will be provided with Spanish-language consent forms and will be consented by a study data collector who is fluent in Spanish. All potential participants will be informed of the study design and interventions, the risks and benefits of participation, their rights and responsibilities as research participants, and alternatives to participation. Participants will be required to sign an informed consent document prior to screening and enrollment. HIPAA authorization to collect and share personal health information within the investigative group is included in the consent form and will be fully explained as part of the

consent process. For those participants who choose to allow us to store blood samples for future analysis of inflammatory markers, a separate sub-study consent will be administered during the baseline visit.

VIII. Confidentiality and Privacy

Confidentiality will be protected by collecting only information needed to assess study outcomes, minimizing to the fullest extent possible the collection of any information that could directly identify subjects, and maintaining all study information in a secure manner. To help ensure subject privacy and confidentiality, two unique study identifiers will appear on the data collection forms. Any collected patient identifying information corresponding to the unique study identifier will be maintained on a linkage file, stored separately from the data. The linkage file will be kept secure, with access limited to designated study personnel. The linking report and personal identifying data will be destroyed within 3 years of completion of the study. This is consistent with accepted practices for data validation and study design, and will enable us to produce an anonymous analytical data set. Data access will be limited to study staff. Data and records will be kept locked and secured, with any computer data password protected. No reference to any individual participant will appear in reports, presentations, or publications that may arise from the study.

IX. Data and Safety Monitoring

The principal investigator will be responsible for the overall monitoring of the data and safety of study participants. The principal investigator will be assisted by other members of the study staff and an independent safety officer ([name]) will be used to adjudicate adverse events and monitor study progress. As weight loss and weight fluctuation have been associated with increased morbidity and mortality, all hospitalizations will be monitored. In addition, potential adverse effects of the intervention specific to physical exercise, primarily injuries and orthopedic conditions, will be monitored. All serious adverse events and unexpected problems will be recorded on adverse event reporting forms, including action taken. A semi-annual report will be compiled and will include a list and summarization of any adverse events. In addition, these reports will address (1) whether adverse event rates are consistent with pre-study assumptions; (2) reason for dropouts from the study; (3) whether all participants met entry criteria; (4) whether continuation of the study is justified on the basis that additional data are needed to accomplish the stated aims of the study; and (5) conditions whereby the study might be terminated prematurely. These reports will be provided to both the study safety officer and the IRB.

A. Reporting of Unanticipated Problems, Adverse Events or Deviations

Any unanticipated problems, serious and/or unexpected adverse events, deviations or protocol changes will be promptly reported by the principal investigator or designated member of the research team to the safety officer, IRB and NIH if appropriate.

Reference List

- (1) Centers for Disease Control and Prevention. National diabetes fact sheet: national estimates and general information on diabetes and prediabetes in the United States, 2011. Atlanta, GA: U.S. Department of Health and Human Services, Centers for Disease Control and Prevention; 2011.
- (3) Centers for Disease Control and Prevention (CDC). Diabetes: Disabling, deadly, and on the rise 2003. National Center for Chronic Disease Prevention and Health Promotion . 2003. Atlanta, Georgia, Department of Health and Human Services.

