The principles guiding the selection of the following inclusion and exclusion criteria are to ensure the enrollment of participants who meet 3 major criteria: 1) high risk for developing diabetes, 2) no medical contraindications to participate in a lifestyle intervention including unsupervised physical activity and weight loss, and 3) ethical randomization, i.e., there are no compelling reasons that potential participants should be referred for immediate weight loss. Subjects will include 225 overweight or obese adults with pre-diabetes in Forsyth County, NC and the surrounding area. All participants will be required to identify themselves as Hispanic or Latino and we hope to recruit approximately equal numbers of men and women based on their representation in the population of the area. As women are more likely to seek medical care than men, we anticipate at least 50% of our sample to be female. We plan to make concerted efforts to ensure that no less than 40% of our sample is male.

a. Inclusion Criteria

- Demographics: Men and women 18 years of age and older who reside in or near Forsyth County, NC.
- Ethnicity: self-identified as Hispanic or Latino
- Evidence of pre-diabetes: HbA1c of 5.7-6.5%
- Body Mass Index (BMI): 25-45 kg/m²
- Willingness to Accept Randomization: Potential participants must be willing to accept randomization to either the intensive lifestyle intervention or the comparison usual care condition.

b. Exclusion Criteria

- Weight Loss: Currently involved in a supervised program for weight loss.
- Diabetes: Clinical history of diabetes mellitus, or newly diagnosed diabetes mellitus at screening.
- Recent History of Cardiovascular Disease: Clinical history of cardiovascular disease (CVD) occurring within the past 6 months, including myocardial infarction, angina, coronary revascularization, stroke, TIA, carotid revascularization, peripheral arterial disease, congestive heart failure. All persons with recent CVD should be participating in cardiac rehabilitation (with appropriate supervision as indicated) to reduce their risk of recurrence; hence, randomization might raise ethical concerns.

[figure not shown]
- Hypertension: Uncontrolled high blood pressure: BP \geq 160/100. Potential participants can be re-screened after control has been achieved.
- Pregnancy: Pregnancy, breast feeding, or planning pregnancy within 2 years.

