9. Have you been diagnosed with or treated for any cancer except (non-melanoma) skin cancer in the last 5 years?

¹ Yes →

PARTICIPANT EXCLUDED

Recent diagnosis and/or treatment of cancer

² No

³ Don't Know

10. Have you ever had any of the following?

your heart stopped and doctors had to restart it with an electric shock or defibrillator

¹ Yes ² No ³ Don't Know

kidney dialysis

¹ Yes ² No ³ Don't Know

implanted defibrillator

¹ Yes ² No ³ Don't Know

major organ transplant

¹ Yes ² No ³ Don't Know

If participant answered yes to any of the above:

PARTICIPANT EXCLUDED
History of major condition/chronic disease

11. Can you walk two blocks (about $\frac{1}{4}$ mile) without stopping without the aid of a cane, crutches, walker or other such device?

¹ Yes

PARTICIPANT EXCLUDED

² No →

Unable to perform moderate intensity exercise

³ Don't Know

12. (If female) Are you currently pregnant or nursing or planning to become pregnant?

¹ Yes →

PARTICIPANT EXCLUDED

² No

Pregnant

³ Male, not applicable

Nursing

Planning pregnancy

13. Have you had any of the following?

Heart Attack

¹ Yes ² No ³ Don't Know

[figure not shown]
Stroke, mini stroke, or TIA

¹ Yes ² No ³ Don't Know

Heart bypass surgery ¹ Yes ² No ³ Don't Know
 Heart angioplasty, balloon surgery
 of the heart, or a stent ¹ Yes ² No ³ Don't Know
 Participated in cardiac rehabilitation ¹ Yes ² No ³ Don't Know

If participant answered yes to any of the above, did it occur in the past six months?

¹ Yes

² No

PARTICIPANT EXCLUDED

Recent history of cardiovascular disease

When was your most recent event?

MONTH

DAY

YEAR

Re-screen 6 months from above date

14. Are you currently taking medications for weight loss or participating in a weight loss program?

¹ Yes

Are you willing to stop taking these medications or
 participating in the other weight loss program for the time
 that you are participating in HELP?

¹ Yes

² No

→ **PARTICIPANT EXCLUDED**

15. Are you currently taking steroid pills or shots such as prednisone or cortisone? (This does not
 include hormone replacement)

¹ Yes

² No

Which ones?

*Contact study doctor for consult before participant can
 continue screening process.*

16. Are you currently being treated for drug or alcohol abuse?

¹ Yes

² No

PARTICIPANT EXCLUDED

Self-Reported substance abuse

17. Have you ever been hospitalized for a major mental disorder or psychiatric problem?

¹ Yes

² No

If "yes", contact study doctor for consult before

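### Item 13 of the Pre-Screening Interview leaves out four of the eight recent cardiovascular conditions that the protocol excludes, and the PAR-Q does not fully make up for it

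*Combined protocol and SAP*

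**What the plan says.** Section III.D.b (Exclusion Criteria) excludes a clinical history of cardiovascular disease in the past 6 months, "including myocardial infarction, angina, coronary revascularization, stroke, TIA, carotid revascularization, peripheral arterial disease, congestive heart failure". It adds that people with recent disease ought to be in cardiac rehabilitation, so that randomising them might be ethically questionable.

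Section III.E.a (Tiered Screening Process) gives the job of assessing medical history to a pre-screening tool. After consent come height, weight, blood pressure, the PAR-Q and finally HbA1c.

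The Pre-Screening Interview is in Appendix B. Its cardiovascular question, "13. Have you had any of the following", lists heart attack, "Stroke, mini stroke, or TIA", "Heart bypass surgery", "Heart angioplasty, balloon surgery" or a stent, and "Participated in cardiac rehabilitation". The time limit follows: "If participant answered yes to any of the above, did it occur in the past six months". A yes there excludes the person and sets a re-screening date.

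On the PAR-Q, section V.B (Protection against Risks) says: "Persons who screen positive will be required to obtain medical clearance from a primary care provider prior to participation". Section VI (Subject Recruitment Methods) repeats the clearance rule. It also words the cardiovascular screen differently, as a recent history of an acute event.

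**The concern.** The criterion and the question that applies it do not match. Staff who work through the interview as printed would not ask by name about half of the conditions that the protocol says must keep a person out.

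The protocol gives its own reasons why this matters. Section III.D opens by requiring that participants have no medical contraindication to unsupervised physical activity and that randomisation be ethical. Section V.A names cardiovascular events as a risk of increased activity in sedentary people. Section III.K counts accurate assessment of eligibility among the things on which the integrity of the trial depends. If people who meet an exclusion are enrolled, there are protocol deviations to report, and the enrolled population differs from the one described.

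**Working it through.** No sample size, power or error-rate figure bears on this point, so the check is a comparison of texts. The inputs are the eight conditions in section III.D.b, item 13 of the Pre-Screening Interview and the seven PAR-Q questions (both in Appendix B).

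| Condition in III.D.b | Named in item 13, with six-month rule | PAR-Q | Result on the visible forms |
|---|---|---|---|
| Myocardial infarction | Yes | not needed | Exclusion |
| Coronary revascularization | Yes (bypass; angioplasty or stent) | not needed | Exclusion |
| Stroke | Yes | not needed | Exclusion |
| TIA | Yes | not needed | Exclusion |
| Angina | No | Indirect: chest pain on exertion (Q2), chest pain at rest in the past month (Q3), heart condition (Q1) | Clearance |
| Congestive heart failure | No | Indirect: heart condition with doctor-restricted activity (Q1), current heart or blood pressure drugs (Q6) | Clearance |
| Carotid revascularization | No | No specific item | Generic items only |
| Peripheral arterial disease | No | No specific item | Generic items only |

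The counts:

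- Named with the six-month exclusion: 4 of 8.
- Not named: 8 − 4 = 4.
- Of those four, reached indirectly by the PAR-Q: 2. With no specific item on any visible form: 4 − 2 = 2.

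The PAR-Q and item 13 also differ in two ways that matter:

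1. **Time window.** The criterion looks back six months. PAR-Q Q3 looks back one month, and Q1, Q2 and Q6 set no look-back period. Someone whose angina was at rest and ended more than a month ago could answer no to Q3.
2. **Consequence.** A yes within six months on item 13 ends eligibility. A yes on the PAR-Q sends the person for medical clearance. Nothing in the documents says that the clearing clinician is told of the six-month rule.

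Two routes to randomisation against section III.D.b follow:

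- A person with angina or heart failure in the past six months screens positive on the PAR-Q, obtains clearance and proceeds.
- A person with carotid revascularization or peripheral arterial disease in the past six months, who has not attended cardiac rehabilitation and answers no on the PAR-Q, meets no question about the condition.

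The baseline visit is not described as a second check. Table 3 lists medical history there, but section III.E.b invites only people who already satisfy the criteria, and they are to be randomised.

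**The case against.** The strongest reply is that one question on a first-tier form is not the whole screening process.

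- **The PAR-Q is itself a screening form.** It asks about chest pain, heart conditions and heart drugs. A reader might infer from item 13 that the four conditions are never asked about at all. The documents do not support that: angina and heart failure are reached, though indirectly.
- **Other items catch some cases.** Item 13 excludes on cardiac rehabilitation within six months, and section III.D.b says that people with recent disease should be in it. Item 11 excludes anyone who cannot walk two blocks without stopping or without an aid, which may catch symptomatic peripheral arterial disease. Item 21 asks for any health reason that would prevent full participation. These are partial catches. The rehabilitation line, for example, misses everyone who did not attend.
- **Section III.H.c promises the history.** It says that cardiovascular history will be obtained at screening to evaluate the criteria. Section III.H says that questionnaires enter Appendix B as they are developed, section III.I puts the detailed procedures in a Manual of Procedures, and the post-consent screening form is visible only from item 5. So it cannot be concluded that the screening process is unable to apply the criterion. Items 5 and 6 of that form (PAR-Q, HbA1c) follow the order in section III.E.a, which suggests that items 1 to 4 hold consent and physical measurements, but that is inference.
- **The interview is coarse by design.** Its BMI limits are 23 to 50, against 25 to 45 in the criteria. But BMI is measured again after consent. No later visible step asks about the four conditions by name.
- **The risk is described as modest.** Activity is moderate and builds up slowly, clearance is a real safeguard, and semi-annual reports check whether participants met entry criteria. A reader might infer that the plan fails on participant safety. The documents do not establish that.

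What stands after all this is the mismatch. No visible form attaches the six-month exclusion to these four conditions, and clearance is a different outcome from exclusion.

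**Conclusion.** The point holds as an inconsistency between the criterion and the form. Four of the eight excluded conditions have no named question with the six-month rule. For two of these four the PAR-Q gives an indirect prompt that leads to clearance, and for the other two there is no specific item. Section VI adds a third description, based on acute events, which is closer to the list in item 13 than to the one in section III.D.b.

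The conclusion assumes that the visible forms are the ones in use, and that neither the unseen items of the post-consent form nor the Manual of Procedures fills the gap. If either does, what remains is to align the printed texts. The number of participants affected cannot be estimated: the documents give no frequency for these conditions and no clearance rate. The change is worth making because the protocol gives safety and ethical reasons for the exclusion and the correction is cheap.

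**What to change.** 1. Check items 1 to 4 of the post-consent form and the Manual of Procedures for questions on the four conditions.
2. Reconcile section III.D.b, section VI and item 13 to a single statement of the cardiovascular criterion. Which conditions it should contain is for the investigators to decide.
3. Make the screening form ask about every condition that the reconciled criterion names, and state the consequence of a yes.
4. Reword the follow-up question. Whether something occurred in the past six months is clear for a procedure or an acute event. It is unclear for angina, peripheral arterial disease or heart failure, which may be long-standing: a person with established disease could truthfully say no. Adding four lines under the present wording would not be enough.
5. State how a positive PAR-Q followed by clearance relates to the exclusion, so that clearance is not read as overriding it unless that is intended.

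The cost is a few lines on an existing interview form, matching edits to two protocol sections, and possibly a few more people excluded or deferred for re-screening. The sample size and the analysis are unchanged.
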